15.2 Analyses

Primary:

The primary analysis is the count of patients alive after 2 months since study entry. If 4 or more patients are alive at the 2 months assessment, the null hypothesis of a 15% survival probability at 2 months will be rejected in favor of our alternative hypothesis of a 60% survival probability. Ninety-five percent confidence intervals will be constructed based upon the exact binomial confidence interval. No loss-to-follow-up or censoring is expected prior to the study's primary endpoint assessment.

Secondary:

There are no formal response criteria for secondary HPS. Therefore, efficacy assessments (including appropriate laboratory studies) will be performed weekly (weeks 1-5), and every two weeks (weeks 6-12), and monthly (after 12 weeks), and responses determined as previously reported in a retrospective study.⁸ Briefly, a complete response is defined as

complete normalization of all quantifiable symptoms and laboratory abnormalities (described in the diagnostic criteria for HPS, above). A partial response is defined as at least a 25% improvement in two or more quantifiable symptoms/laboratory markers following the initiation of treatment. The best overall response is the best response recorded from the start of the treatment until disease progression/recurrence

Follow-up time will be calculated from the first administration of ruxolitinib, until death for OS or until disease-progression or death for PFS. Patients lost to follow-up will be censored on the date of their last known clinical assessment. Specifically for DOR, only patients having at least a PR to therapy are evaluable. Duration will be calculated from the date of the determination of partial response or better until the date of progression, death, or additional non-protocol therapy. Again, for patients lost to follow-up, duration will be censored at the time of last clinical assessment. The count and percentage of the number having an objective response (CR, CRu, or PR) will be reported along with confidence intervals. Product-limit estimates of Kaplan and Meier will be used to estimate OS, PFS, and DOR. The likelihood of loss to follow-up is expected to be extremely low.

Exploratory:

Plasma will be obtained before treatment and weekly thereafter, and cryopreserved for future corollary studies (e.g. cytokine^{27,28} and soluble CD163 determination³⁴). We will compare cytokine, soluble IL-2R and soluble CD163 levels pre-treatment and post treatment. We seek to correlate change in expression (decrease) with positive response (complete vs. partial vs. stable) to therapy via regression models that appropriately account for the serial correlation of repeated measures within a patient. Inference from these models would be hypothesis generating.

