3.4 Expected Duration of Subject Participation

3.4.1 Duration of Therapy

In the absence of treatment delays or cessation due to adverse events, treatment may continue indefinitely or until one of the following criteria applies:

- Disease progression.
- Intercurrent illness that prevents further administration of treatment.
- The investigator considers it, for safety reasons, to be in the best interest of the patient. The investigator may recommend gradual discontinuation (i.e. ruxolitinib taper) in patients achieving a prolonged response (defined as a PR or CR ≥ 6 months in duration). The rate of a ruxolitinib taper, and decisions to dose escalate in the setting of recurrent signs/symptoms, are not specified in this protocol, and are at the discretion of the investigator.
- Unacceptable adverse events such as any toxicity or other issue that causes a delay of study drug administration by more than 4 weeks.
- General or specific changes in the patient's condition render the patient unacceptable for further treatment in the judgment of the investigator.
- Patient decision to withdraw from treatment (partial consent) or from the study (full consent).

- Death.
- Sponsor reserves the right to temporarily suspend or prematurely discontinue this study.

The date and reason for discontinuation must be documented. Every effort should be made to complete the appropriate assessments.

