3.4.2 Duration of Follow Up

Patients will be followed for efficacy and toxicity for 30 days after treatment has been discontinued. Thirty days after treatment discontinuation, progression-free and overall survival will be collected every 6-12 months by a review of the clinical notes from the treating investigator or other provider. Patients will be followed for up to five years or until the end of the study or death, whichever occurs first.

Serious adverse events that are still ongoing at the end of the study period will necessitate follow-up to determine the final outcome. Any serious adverse event that occurs after the study period and is considered to be possibly related to the study treatment or study participation will be recorded and reported immediately per IRB & FDA reporting guidelines.

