13. MEASUREMENT OF EFFECT

13.1 Response evaluation

13.1.1 Definitions

Evaluable for toxicity. All patients will be evaluable for toxicity from the time of their first treatment with Ruxolitinib.

Evaluable for objective response. Only those patients who received at least 7 days of therapy, and have had their disease re-evaluated will be considered evaluable for response. These patients will have their response classified according to the definitions stated below.

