13.1.3 Response Criteria

Evaluation of Response

Response	Evaluation of Target Lesions
Complete Response (CR)	Complete normalization of all quantifiable signs and laboratory abnormalities included in the diagnostic criteria for HPS.
Partial Response (PR)	At least a 25% improvement in two or more quantifiable signs/laboratory markers.
Progressive Disease (PD)	At least a 50% worsening in two or more quantifiable signs/laboratory markers.
Stable Disease (SD)	Neither sufficient improvement to qualify for CR/PR, nor sufficient worsening to qualify for PD.

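### The window for best overall response in Section 15.2 does not close when other HPS therapy starts, so an improvement after a switch can count towards the ruxolitinib response rate

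*Combined protocol and SAP*

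**What the plan says.** The rule for best overall response is in Section 15.2 (Secondary): "The best overall response is the best response recorded from the start of the treatment until disease progression/recurrence". The response rate is built on it: "The count and percentage of the number having an objective response (CR, CRu, or PR) will be reported along with confidence intervals". Partial response requires "at least a 25% improvement in two or more quantifiable symptoms/laboratory markers following the initiation of treatment".

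For duration of response, the same section uses a different end point. Duration runs "until the date of progression, death, or additional non-protocol therapy". Section 13.1.4 also defines duration of response, but ends it only at recurrent or progressive disease and does not mention other therapy.

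Four further provisions bear on the point:

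- Section 13.1.3 sets progressive disease at: "At least a 50% worsening in two or more quantifiable signs/laboratory markers".
- Section 13.1.1 defines the evaluable set: "Only those patients who received at least 7 days of therapy, and have had their disease re-evaluated will be considered evaluable for response".
- Section 3.4.1 lists reasons for stopping other than progression, among them intercurrent illness, investigator judgment, patient decision and "Unacceptable adverse events such as any toxicity or other issue that causes a delay of study drug administration by more than 4 weeks".
- Section 3.4.2 says: "Patients will be followed for efficacy and toxicity for 30 days after treatment has been discontinued". Section 6.3 describes the same 30 days as follow-up for toxicity and does not mention efficacy.

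**The concern.** The secondary objective in Section 2.2 is the response rate in patients treated with ruxolitinib. To be read as activity of ruxolitinib, that rate should rest on assessments made before another active treatment begins. As written, the window stays open across a change of treatment unless progression has been documented first.

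A change of treatment is plausible here. Sections 1.1 and 1.3 describe etoposide and steroids as the usual approach in adults, so a patient who comes off ruxolitinib with active disease may well receive them. The threshold for partial response is modest and could be met on the next therapy.

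At stake are the reported response rate and the exploratory models in Section 15.2 that relate biomarker change to response category. The go/no-go rule is not involved, because it rests only on the number alive at 2 months.

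**Working it through.** The plan gives no target, power or threshold for the response rate, so there is no planned figure to reproduce. The check has two parts: whether the written rules allow the case, and what one such case does to the estimate.

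**1. Is the case reachable?** Take an illustrative patient with stable disease who stops ruxolitinib for toxicity on day 10, starts another HPS regimen on day 12, and on day 30 shows two markers improved by 25%.

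- Evaluable (13.1.1)? Yes. The patient had at least 7 days of therapy and was re-evaluated. Nothing requires the re-evaluation to precede new therapy.
- Window already closed (15.2, 13.1.3)? No. Only progression or recurrence closes it, and this patient has not worsened by 50% in two markers.
- Still under efficacy follow-up (3.4.2)? Yes. It runs to day 10 + 30 = day 40, and the assessment is on day 30.
- Partial response met (15.2)? Yes, at 25% in two markers after treatment started.

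The rules as written make this patient a responder. Had progression been recorded before day 12, the window would already be closed and the problem would not arise.

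**2. Direction.** Best overall response is a maximum over the window. For a fixed set of evaluable patients, lengthening the window can add a responder or upgrade a PR to a CR, but cannot remove a response. A patient already in PR before the switch does not change the response rate.

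**3. Size.** One extra responder adds 1/n to the rate. With all 10 patients evaluable (sample size from Section 15.1), that is 1/10 = 10 percentage points. If only 8 were evaluable under 13.1.1 (an assumed number), it would be 1/8 = 12.5 points.

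Exact (Clopper-Pearson) 95% intervals, with responder counts chosen only for illustration:

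| Responders / evaluable | Rate | 95% CI |
|---|---|---|
| 3/10 | 30% | 6.7–65.2% |
| 4/10 (one post-switch responder added) | 40% | 12.2–73.8% |
| 5/10 (two added) | 50% | 18.7–81.3% |

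**4. Frequency.** The miscount needs a chain of events: at least 7 days on drug, no earlier PR, stopping without progression, starting other therapy, then improving and being assessed. The documents give no rate for any link, so none is estimated here.

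**The case against.** Several points can fairly be made on the other side.

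*The plan is silent rather than wrong.* A reader might infer that the plan directs analysts to credit ruxolitinib with responses to the next therapy. It contains no such instruction. Section 15.2 refers elsewhere to response to therapy, which suggests that response to ruxolitinib was intended. Even so, the window has a stated end, and new therapy is not part of it. Applied literally, it admits the case above.

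*Exposure is narrow.* This stands. Section 6.3 mentions only toxicity for the 30 days after stopping. The calendar in Section 12.2 has no post-discontinuation visit, and its footnote 4 ties the later response procedures to patients still on treatment. After 30 days, Section 3.4.2 collects only progression-free and overall survival. These provisions limit how often a late assessment would exist. They do not say it would be disregarded.

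*The two rules in 15.2 need not contradict each other.* A reader might infer that they do, because the example patient's duration of response would end on day 12, before the response is seen on day 30. The text does not establish this. Duration is restricted to patients with at least a PR to therapy. If therapy there means ruxolitinib, this patient is not evaluable for duration and no conflict arises. The supported statement is that the two definitions are not aligned.

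*A probability of miscounting is not available.* It is tempting to assume that 10% or 20% of patients would be affected and to report 1 − 0.9^10 = 65% or 1 − 0.8^10 = 89% as the chance of at least one miscount. Those figures only restate the assumed rate. With weekly assessments in weeks 1–5 and a low PR threshold, many patients may reach PR before any switch.

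*The consequence is small.* The endpoint is secondary and has no threshold, and its interval is wide at n = 10. That limits the weight of the point but does not justify leaving the window open.

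Finally, Section 15.2 says responses follow a cited retrospective study. Any cut-off given there cannot be seen from these documents.

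**Conclusion.** The point holds as a correctable gap in a secondary endpoint. Section 15.2 closes best overall response only at progression or recurrence, so a patient who switches treatment without progressive disease can enter the ruxolitinib response rate on a post-switch assessment. For a given set of evaluable patients the bias can only be upward. The 10-point step per patient assumes that all 10 are evaluable; it is larger if fewer are. The number of patients affected is unknown and could be zero. The exposure lies mainly in the 30 days after ruxolitinib stops, and depends on whether efficacy is in fact assessed then, on which Sections 3.4.2 and 6.3 differ. A misclassified response would carry into the exploratory response correlations. The sample size and the 2-month survival rule are unaffected.

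**What to change.** In Section 15.2, define best overall response as the best response from first dose until the earliest of progression or recurrence, death, or the start of non-protocol HPS-directed therapy. Count patients with no CR or PR before that date as non-responders, and list improvements first seen after a switch separately.

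Four accompanying edits are needed:

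- Align the duration-of-response definition in 13.1.4 with 15.2.
- State which on-study treatments count as non-protocol HPS therapy for this analysis. Corticosteroids need explicit mention, because Section 4.2 exempts them from the prior-therapy exclusion and no section says how on-study use is treated in the response analysis.
- Reconcile Sections 3.4.2 and 6.3 on whether the 30-day follow-up covers efficacy.
- Record the start date of any such therapy through that follow-up. Section 6.2 requires concurrent drugs on the case report form because of possible interactions, but does not clearly cover treatment begun after ruxolitinib stops.

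The cost is a few sentences and one extra date per patient. The reported response rate may be slightly lower.

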6.3 Duration of Follow Up

Patients will be followed for toxicity for 30 days after treatment has been discontinued or until death, whichever occurs first. Patients will be followed for survival for up to five years or until the end of the study or death, whichever occurs first.

The clinical course of each event will be followed until resolution, stabilization, or until it has been determined that the study treatment or participation is not the cause for a maximum of 6 months.

Serious adverse events that are still ongoing at the end of the study period will necessitate follow-up to determine the final outcome. Any serious adverse event that occurs after the study period and is considered to be possibly related to the study treatment or study participation will be recorded and reported immediately per IRB and FDA reporting guidelines.

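### For patients lost to follow-up, overall survival is censored at the last clinical assessment and not at the last date known alive (minor, free to improve)

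*Combined protocol and SAP*

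**What the plan says.** Section 15.2 (Secondary) defines the two survival times in one sentence: "Follow-up time will be calculated from the first administration of ruxolitinib, until death for OS or until disease-progression or death for PFS". The next sentence sets the censoring date: "Patients lost to follow-up will be censored on the date of their last known clinical assessment". It makes no distinction between the endpoints, so it covers OS as well as PFS. A similar assessment-based date is then given for duration of response. The estimator is stated as "Product-limit estimates of Kaplan and Meier will be used to estimate OS, PFS, and DOR".

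Two sections describe how late survival data arise. Section 3.4.2 ends efficacy and toxicity follow-up 30 days after treatment stops. From then on, "progression-free and overall survival will be collected every 6-12 months by a review of the clinical notes", and those notes may be the treating investigator's or another provider's. Section 6.3 adds: "Patients will be followed for survival for up to five years".

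On loss to follow-up, section 15.2 says of the primary endpoint: "No loss-to-follow-up or censoring is expected prior to the study's primary endpoint assessment". Of the secondary endpoints it says: "The likelihood of loss to follow-up is expected to be extremely low".

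No section defines a last-known-alive date, and none gives a censoring date for patients who are alive and still followed when the data are cut.

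**The concern.** For PFS, a patient is known to be progression-free only as far as the last examination that could have shown progression, so an assessment date is right. For OS, the patient is known to be event-free up to the last date on which anything shows that he or she was alive. Section 15.2 uses the PFS date for both.

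The follow-up scheme leaves room for the two dates to differ. Once the 30 days after treatment have passed, survival is read from notes at intervals of 6 to 12 months. A review may turn up an entry that shows the patient alive but is not an assessment. If that patient is later lost, the rule as worded stops the OS time at the earlier date.

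At stake is the accuracy of a descriptive secondary curve based on ten patients, and whether the censoring date is settled in advance or chosen by the analyst after seeing the data.

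**Working it through.** The plan gives no figure for this point, so there is none to reproduce. The sizes below rest on assumed data.

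**Inputs from the documents.** Ten patients and a threshold of 4 alive at 2 months (section 15.1); OS from first dose to death, Kaplan-Meier estimation, and censoring of lost patients at the last clinical assessment (section 15.2); 30 days of follow-up after treatment, then review of notes every 6 to 12 months (section 3.4.2).

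**1. Direction.** At a death time with n patients at risk and d deaths, the Kaplan-Meier factor is 1 − d/n. Moving one patient's censoring date earlier removes that patient from the risk set at every death between the two dates. The factor there becomes 1 − d/(n − 1), which is smaller. All other factors are unchanged. The estimate therefore falls if a death lies between the two dates, and otherwise stays the same.

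**2. Size at 6 months (assumed data).** Ten patients: deaths on days 10, 20, 30, 35, 90 and 150; three alive at day 365; one lost patient last assessed on day 50 and known alive on day 200. After the first four deaths, S = 6/10 = 0.60 with six at risk.

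- Censored at day 50, as written: five at risk on day 90 and four on day 150. S(180) = 0.60 × 4/5 × 3/4 = 0.36.
- Censored at day 200, last known alive: six at risk on day 90 and five on day 150. S(180) = 0.60 × 5/6 × 4/5 = 0.40.

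The difference is 4 percentage points. At day 61 both rules give 0.60, because no death falls between day 50 and day 61.

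**3. Size at 2 months (assumed data).** Suppose 6 of 10 have died and 4 are alive at 2 months, and one of the four is censored before 2 months. Let k be the number of deaths between that censoring date and 2 months. Then

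S = (4 + k)/10 × 3/(3 + k).

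| k | 0 | 1 | 2 | 3 | 4 | 5 | 6 |
|---|---|---|---|---|---|---|---|
| S | 0.400 | 0.375 | 0.360 | 0.350 | 0.343 | 0.338 | 0.333 |

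With the last-known-alive date, S = 4/10 = 0.400. The largest fall is 0.400 − 0.333 = 0.067, or 6.7 points. For scale, the exact 95% interval for 4 of 10 is 0.122 to 0.738.

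**4. Can this arise before 2 months?** A patient who stops treatment on day 20 has protocol follow-up to day 20 + 30 = 50. If a contact that is not an assessment shows the patient alive on day 61, and the patient is then lost, the primary analysis counts a survivor while the OS curve censors at day 50. This is possible, but it needs early discontinuation, later loss and a non-assessment source together.

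**5. Primary analysis.** It is a count: "The primary analysis is the count of patients alive after 2 months since study entry". No censoring date enters it, so the count, its exact interval and the 4-of-10 rule are the same under either rule.

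**The case against.** The strongest reply is that the two dates may hardly ever differ. The rule refers to a clinical assessment and does not restrict it to a scheduled study visit. The only late source of survival data that the plan names is clinical notes, including those of other providers, and a dated provider note would often count as a clinical assessment. The plan mentions no telephone contact or registry. It also expects no loss before 2 months and very little afterwards. All of this stands, and it is why the point is minor. It does not remove the point: a note can show that a patient is alive without recording an assessment, and the plan does not say how such an entry is to be dated.

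Three stronger readings are tempting, and the documents do not support them.

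- A reader might infer that OS as a whole is censored this way. The rule covers only patients lost to follow-up.
- A reader might infer a built-in bias, with deaths counted from any source and survival credited only from assessments. Section 15.2 does not limit how a death is learned of, but after the 30 days section 3.4.2 names the same notes as the source for both. Time is dropped only if a later known-alive date exists.
- A reader might infer that the OS curve will contradict the primary result at 2 months. Section 15.2 refers to an assessment at 2 months, and a patient seen alive then would not be censored earlier. The case in step 4 is an edge case, and even then the estimate moves only if a death falls in the gap.

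**Conclusion.** The point holds in a limited form. For lost patients, section 15.2 applies to OS a censoring date that belongs to PFS, and it is silent on patients alive at data cut-off. Where a lost patient is known alive after the last assessment, survival time is dropped and the OS estimate can only fall or stay the same. In the assumed examples one patient costs 4 points at 6 months and at most 6.7 points at 2 months. Both are small beside the uncertainty of a ten-patient estimate. With no loss to follow-up, or if every later record is a clinical assessment, the lost-patient rule has no effect. No decision in the plan depends on it. It is a minor improvement that costs almost nothing.

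**What to change.** In section 15.2, replace the shared sentence with one rule for each endpoint:

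- *OS: a patient not known to have died is censored at the last date, up to data cut-off, on which any source shows the patient alive. This applies both to patients lost to follow-up and to those still followed.*
- *PFS: a patient without progression or death is censored at the last assessment at which progression could be judged.*

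Add a last-known-alive date and its source to the survival form, so that the periodic review of notes records it. The cost is one sentence and one form entry. Sample size, error rates, the primary count and patient treatment do not change.

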2.3 Exploratory Objectives

To assess inflammatory cytokines and markers of T-cell/macrophage activation (i.e. cytokines, sIL-2R, sCD163) as predictive biomarkers.

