4.1 Inclusion Criteria

Patients must meet all of the following inclusion criteria to be eligible for enrollment:

1. Patients, or their legally authorized representative, must voluntarily provide written IRB-approved informed consent.
2. Males and females, 18 years of age or older at the time of enrollment.
3. Patients must meet the diagnostic criteria for HPS (at least 5 of the following):
 - fever
 - splenomegaly
 - cytopenia involving ≥ 2 cell lines (Hemoglobin < 9 g/dL; platelets $< 100,000/\mu\text{L}$; absolute neutrophil count $< 1000/\mu\text{L}$)
 - hypertriglyceridemia or hypofibrinogenemia
 - tissue demonstration of hemophagocytosis
 - low or absent NK cell activity
 - serum ferritin ≥ 3000 ug/L
 - soluble IL-2 receptor (CD25) > 2400 U/mL.
4. In the investigator's opinion, the patient has the ability to participate fully in the study and comply with all its requirements.

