13.1.2 Disease Parameters

- Fever
- Splenomegaly (by physical examination or radiographic imaging).
- Cytopenias involving ≥ 2 cell lines
- Ferritin
- Triglycerides
- Fibrinogen
- Soluble IL-2 receptor
- NK cell activity

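### Section 15.2 relates the fall in sIL-2R to a response that sIL-2R helps define, and the response levels for all markers leave out progression and the earliest deaths

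*Combined protocol and SAP*

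**What the plan says.** Section 2.3 sets out to assess cytokines, sIL-2R and sCD163 "as predictive biomarkers". Section 15.2 (Exploratory) gives two analyses. The first is a before-and-after comparison: "We will compare cytokine, soluble IL-2R and soluble CD163 levels pre-treatment and post treatment". The second relates marker change to outcome: "We seek to correlate change in expression (decrease) with positive response (complete vs. partial vs. stable) to therapy via regression models". The models are to allow for repeated measures within a patient, and the inference is described as hypothesis generating.

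Response is defined elsewhere. Section 13.1.2 lists eight disease parameters, one of which is "Soluble IL-2 receptor". Section 4.1 has the same marker among the diagnostic criteria: "soluble IL-2 receptor (CD25) > 2400 U/mL". In section 13.1.3, CR is "Complete normalization of all quantifiable signs and laboratory abnormalities included in the diagnostic criteria for HPS", PR is "At least a 25% improvement in two or more quantifiable signs/laboratory markers", and PD is "At least a 50% worsening in two or more quantifiable signs/laboratory markers". Section 13.1.1 counts a patient as evaluable for response only after at least 7 days of therapy and a disease re-evaluation.

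**The concern.** There are two separate problems.

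First, the sIL-2R model has the same measurement on both sides. A fall in sIL-2R helps a patient qualify as a responder, and the model then asks whether responders had a larger fall. Some positive association is expected from the definition alone. sCD163 and the cytokines have no such advantage. If the three are compared and the strongest is carried into the expanded cohort foreseen in section 15.1, sIL-2R starts ahead. The hypothesis-generating label warns of chance and imprecision, but it does not tell a reader that one marker is favoured by construction.

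Second, the response scale in the model runs only from complete to stable. Patients whose disease worsens from the start have no level, and those who die before re-evaluation have no response at all. For every marker, the contrast loses the patients with the worst outcomes.

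**Working it through.** The plan gives no sample size, power or effect size for this analysis, so there is no figure to reproduce. The check traces the definitions and then sizes the overlap under stated assumptions.

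**Overlap by definition**

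| Marker in the 15.2 model | Diagnostic criterion (4.1) | Response parameter (13.1.2) |
|---|---|---|
| sIL-2R | yes | yes |
| sCD163 | no | no |
| Cytokines | no | no |

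Nothing in 15.2 recomputes response without sIL-2R. The text does not say which variable is the dependent one, but the overlap exists either way. Modelling serial correlation does not remove it.

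**Size of the built-in association**

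Assumptions, none from the documents: k quantifiable markers, independent of each other, each with chance q of a 25% improvement; CR and PD ignored. PR needs at least two improved markers, so:

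- if sIL-2R improved, one more is enough: P(PR) = 1 − (1−q)^(k−1)
- if it did not, two others are needed: P(PR) = 1 − (1−q)^(k−1) − (k−1)·q·(1−q)^(k−2)

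For k = 8 (the length of the 13.1.2 list) and q = 0.30:

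- improved: 1 − 0.7^7 = 1 − 0.0824 = 0.918
- not improved: 0.918 − 7 × 0.3 × 0.7^6 = 0.918 − 0.247 = 0.671
- odds ratio: (0.918/0.082) ÷ (0.671/0.329) = about 5.5

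| k | q | P(PR), sIL-2R improved | P(PR), not improved | Odds ratio |
|---|---|---|---|---|
| 5 | 0.2 | 0.590 | 0.181 | 6.5 |
| 5 | 0.3 | 0.760 | 0.348 | 5.9 |
| 7 | 0.3 | 0.882 | 0.580 | 5.4 |
| 8 | 0.2 | 0.790 | 0.423 | 5.1 |
| 8 | 0.3 | 0.918 | 0.671 | 5.5 |
| 8 | 0.5 | 0.992 | 0.938 | 8.5 |

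For k from 5 to 8 and q from 0.2 to 0.5, the odds ratio runs from 5.1 to 8.5, although no marker is related to any other.

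**Same question with continuous change**

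A simulation used 5, 6 or 8 independent log-changes (mean 0 or −0.2, SD 0.4 or 0.7, all assumed), with PR and PD as in 13.1.3 and PD dropped as in 15.2. The correlation of the sIL-2R fall with PR versus SD was 0.02 to 0.26. With sIL-2R removed from the response definition it was about 0.00. A marker outside the definition, standing for sCD163, showed about 0.00 throughout. The direction agrees with the calculation above, but on this scale the artefact is modest.

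**What 10 patients would show**

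Under the same independence model, with a two-sided Fisher exact test of improvement against PR in 10 patients:

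| k | q | P(p < 0.05) | P(estimate in the positive direction) |
|---|---|---|---|
| 8 | 0.3 | 1% | 79% |
| 7 | 0.3 | 2% | 81% |
| 5 | 0.2 | 7% | 69% |
| 5 | 0.3 | 8% | 84% |

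The estimate is tilted upward, but a significant false result is uncommon.

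**Patients who drop out**

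Section 15.1 expects about 15% survival at 2 months under standard care, and the alternative is 60%. Expected deaths by 2 months are 10 × 0.85 = 8.5 and 10 × 0.40 = 4.0. Assuming a constant hazard and 61 days in 2 months, deaths by day 7 are 10 × (1 − S^(7/61)):

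- S = 0.15: 2.0 of 10
- S = 0.60: 0.6 of 10

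The series cited in section 1.3 reports deaths from day 5 after diagnosis, so losses this early are plausible. Primary progressors are lost in addition. The documents give no expected PD rate, so that part cannot be sized.

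**The case against.** The strongest reply is that this is an exploratory analysis in at most 10 patients, labelled as such, with no test level and no decision attached. The go/no-go rule uses 2-month survival only. That stands, and it sets the severity.

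Five stronger readings are tempting, and the documents do not support them.

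- *The whole biomarker analysis is circular.* Only the sIL-2R-versus-response model is. sCD163 and the cytokines are outside the response criteria, and neither the before-and-after comparison nor the pStat1 work in 11.2 is affected.
- *CR always requires sIL-2R to normalise.* Entry needs any five of eight criteria, so a patient can enter with sIL-2R below the threshold. PR can also be reached on two other markers.
- *The plan will produce a false sIL-2R finding.* With 10 patients the artefact is a tilt in the estimate, seldom a significant result.
- *The odds ratio of 5 to 8.5 is what the planned model would show.* It comes from a yes/no version of sIL-2R change and independent markers. The plan models serial values, and the continuous version gave correlations of at most 0.26.
- *All progressors and deaths are excluded.* The omission of PD is explicit in the listed levels. The loss of early deaths is not written in 15.2; it follows from 13.1.1. A patient who dies after a re-evaluation keeps a response category. If best overall response is used, so does one who progresses after SD or PR.

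What remains is that the overlap and the missing lowest level are in the text, and the hypothesis-generating label corrects neither.

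**Conclusion.** The point holds in limited form and is minor. The sIL-2R-versus-response model is partly circular, which pushes its association upward and favours sIL-2R over the other markers. The illustrative odds ratio of about 5 to 8.5 rests on assumed independence, 5 to 8 markers and improvement chances of 20% to 50%. The documents supply none of these chances, so the figure shows direction and rough scale only. For all markers, the response levels leave out primary progressors and, through the evaluability rule, the earliest deaths (about 0.6 to 2.0 of 10 by day 7 under a constant hazard).

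A reader might infer that the trial's main conclusion is at risk. It is not: the primary analysis counts patients alive at 2 months and uses neither response nor biomarkers.

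**What to change.** In section 15.2 (Exploratory):

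1. For the sIL-2R model, compute response from the other parameters only, or report sIL-2R against response descriptively without a model.
2. For all markers, add PD or death before re-evaluation as the lowest response level. A patient who dies before the first post-treatment sample has no change value. State that such patients are counted and described, and that they enter only analyses of the pre-treatment level.
3. Optionally, add 2-month survival as an outcome with the pre-treatment level as predictor, in all treated patients. Use early change only among patients alive with a first post-treatment sample, as a landmark analysis at about day 7. The two must be kept apart, because a model of change cannot include every treated patient.

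The cost is a few sentences in 15.2 and slightly more analysis work. No new samples or visits are needed. With 10 patients the added estimates will be imprecise, and the text should say so.
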